# 11.44 Overall objective status

The overall objective status for an evaluation is determined by combining the patient's status on target lesions, target lymph nodes, non-target lesions, non-target lymph nodes, and new disease as defined in the following tables:

Target Lesions & Target Lymph Nodes	Non-Target Lesions & Non-Target Lymph Nodes	New Sites of Disease	Overall Objective Status
CR	CR	No	CR
CR	Non-CR/Non-PD	No	PR
PR	CR Non-CR/Non-PD	No	PR
CR/PR	Not All Evaluated*	No	PR
SD	CR Non-CR/Non-PD Not All Evaluated*	No	SD
Not all Evaluated	CR Non-CR/Non-PD Not All Evaluated*	No	Not Evaluated (NE)
PD	Unequivocal PD CR Non-CR/Non-PD Not All Evaluated*	Yes or No	PD

Target Lesions & Target Lymph Nodes	Non-Target Lesions & Non-Target Lymph Nodes	New Sites of Disease	Overall Objective Status
CR/PR/SD/PD/Not all Evaluated	Unequivocal PD	Yes or No	PD
CR/PR/SD/PD/Not all Evaluated	CR Non-CR/Non-PD Not All Evaluated*	Yes	PD

\*See Section 11.431

# 11.45 Symptomatic Deterioration

Patients with global deterioration of health status requiring discontinuation of treatment without objective evidence of disease progression at that time, and not either related to study treatment or other medical conditions, should be reported as PD due to "symptomatic deterioration." Every effort should be made to document the objective progression even after discontinuation of treatment due to symptomatic deterioration. A patient is classified as having PD due to "symptomatic deterioration" if any of the following occur that are not either related to study treatment or other medical conditions:

- Weight loss >10% of body weight.
- Worsening of tumor-related symptoms.
- Decline in performance status of >1 level on ECOG scale.

# **12.0** Descriptive Factors: None

# 13.0 Treatment/Follow-up Decision at Evaluation of Patient

# **13.1** Continuation of treatment

Patients who have not had disease progression and have experienced acceptable toxicity are to continue treatment per protocol until confirmed PD, unacceptable toxicity or refusal. And then they will go to event monitoring until death or a maximum of 5 years post-registration.

# **13.2 Progressive Disease (PD)**

The first instance in which a patient's disease status meets the RECIST criteria for PD will continue two additional cycles of treatment per protocol and then undergo disease revaluation. If the initial documented progression is not confirmed by this scan, patients will continue treatment per protocol. If the initial documented progression is confirmed by this scan, patients will go to the event-monitoring phase until death or a maximum of 5 years post-registration.

# Exception: Patients who develop PD in the CNS should discontinue study treatment and go to Event Monitoring.

# **13.3** Criteria for discontinuation of protocol therapy include:

• Disease progression: Where disease progression is: the development of a new metastatic lesion or an objective status of disease progression (as defined by RECIST criteria) on two consecutive evaluations at least 6 weeks apart (Section 13.2).

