# **11.0** Treatment Evaluation

# 11.1 Treatment evaluation using RECIST 1.1 guidelines

The first scan after treatment initiation will be performed at the completion of Cycle 4; scans will be then performed at the completion of every fourth cycle of treatment until disease progression is confirmed or withdrawn of consent. If a patient experiences PD yet continues protocol treatment, the next imaging should take place 2 cycles after the imaging showing PD. If that patient continues on protocol treatment, imaging should then take place every 4 cycles (See Section 4.0).

Disease progression for this protocol is defined as meeting the RECIST criteria for disease progression on two consecutive evaluations at least 6 weeks apart.

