16.34 Progression-free survival (PFS)

Time from randomization to the first 2 consecutive evaluations approximately 6 weeks apart documenting disease progression. The distribution of progression-free survival times will be estimated using the Kaplan-Meier approach.

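### PFS counts only progression seen on two consecutive evaluations, but no second scan is scheduled after CNS progression or symptomatic deterioration, so these progressors may be missed or dated late

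*Combined protocol and SAP*

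**What the plan says.** Section 11.1 sets the general definition: "Disease progression for this protocol is defined as meeting the RECIST criteria for disease progression on two consecutive evaluations at least 6 weeks apart". Section 16.34 defines PFS in the same terms: "Time from randomization to the first 2 consecutive evaluations approximately 6 weeks apart documenting disease progression". It then says: "The distribution of progression-free survival times will be estimated using the Kaplan-Meier approach". It has no censoring rule, does not list death as an event, and does not say which of the two evaluations gives the event date.

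Section 13.2 supplies the second evaluation in the ordinary case. A patient at first RECIST PD "will continue two additional cycles of treatment per protocol and then undergo disease revaluation". CNS progression is the printed exception that follows: "Patients who develop PD in the CNS should discontinue study treatment and go to Event Monitoring". The exception is repeated among the discontinuation criteria in Section 13.3.

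Section 11.45 covers "Patients with global deterioration of health status requiring discontinuation of treatment without objective evidence of disease progression at that time". These patients are to be reported as PD, and the section asks for best efforts to document objective progression afterwards.

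Section 4.1 ties imaging to treatment cycles and ends with an end-of-treatment scan. Section 4.2, the event monitoring table, lists contacts every 3 months until PD, at PD, and every 6 months after PD. It has no imaging row.

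**The concern.** The PFS definition depends on a confirmatory evaluation, and the protocol takes two kinds of progressor off the path that produces it. Section 16.34 does not say what happens to them. Section 11.45 calls symptomatic deterioration PD, while Sections 11.1 and 16.34 taken literally do not.

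The affected patients have new or growing brain disease, or decline severe enough to stop treatment. Leaving them out of the event count would not be neutral: they are removed because they progressed, so the loss is informative and pushes the PFS estimate upward. Because Section 16.34 omits death, a later death would not bring them back either. Median PFS is a named secondary objective (Section 2.22). Without a rule, the analyst has to choose one after seeing the data.

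**Working it through.** **1. The plan's own design figure.** Section 16.2 gives n = 33, null response rate 12%, alternative 30%, one-sided level 0.10 and 90% power. With an exact binomial test:

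- P(X ≥ 6 | 0.12) = 0.198, which exceeds 0.10.
- P(X ≥ 7 | 0.12) = 0.0930, so the rule is to reject at 7 or more responses.
- P(X ≥ 7 | 0.30) = 0.9056.

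The stated figures reproduce. PFS does not enter them. The documents state no target, event count or precision for PFS, so there is no PFS figure to reproduce.

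**2. Does each group reach a second evaluation?**

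| Initial progression | What the protocol does next | Second evaluation scheduled? |
|---|---|---|
| RECIST PD outside the CNS | Two more cycles, then rescan (13.2): 2 × 21 = 42 days = 6 weeks | Yes |
| PD in the CNS | Treatment stops; event monitoring (exception to 13.2) | No |
| Symptomatic deterioration | Treatment has stopped; reported as PD (11.45) | No; best effort only |

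The two-cycle rescan in Sections 4.1 and 11.1 applies to a patient who continues protocol treatment. The end-of-treatment scan has a window of ±7 days, so it does not by itself supply an evaluation 6 weeks after the first.

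**3. Possible size.** Assumptions, none of them in the documents: PFS is exponential with hazard λ; a share f of progressions, unrelated to timing, falls in the two groups; each such patient is censored at first PD; none is confirmed later; there is no other censoring.

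- True median: m = ln 2 / λ.
- Hazard that Kaplan-Meier then estimates: (1 - f)λ.
- Apparent median: ln 2 / [(1 - f)λ] = m / (1 - f).

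For illustration, take m = 22 weeks, the pembrolizumab background figure in Section 1.2 (not a design assumption of this trial), and 33 patients who all progress:

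| f | 1/(1-f) | Apparent median (weeks) | Simulated median (n = 33, 4,000 runs) | Expected events, 33(1-f) |
|---|---|---|---|---|
| 10% | 1.11 | 22/0.9 = 24.4 | 24.5 | 29.7 |
| 20% | 1.25 | 22/0.8 = 27.5 | 27.8 | 26.4 |
| 30% | 1.43 | 22/0.7 = 31.4 | 31.3 | 23.1 |

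Counting every such progression as an event at its first date restores 22 weeks. If the patients were instead carried forward as event-free beyond first PD, the inflation would be larger. If some were confirmed later, it would be smaller for the same f, with those events dated late.

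**The case against.** A reader might infer that these progressors can never become PFS events. The documents do not support that. Section 11.45 asks for objective documentation after treatment stops. Section 11.1 describes scans as running until progression is confirmed. Section 4.2 keeps 3-monthly monitoring until PD, and Section 18.5 requires imaging reports for patients who progress after study therapy. Confirmation is therefore possible. What stands against this is that none of it schedules a second scan: Section 11.1 ties its scans to treatment cycles, which a patient off treatment no longer has, and later documentation gives a later date.

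A reader might also infer that the protocol everywhere demands two evaluations. Section 13.3 can be read as making a new metastatic lesion sufficient on its own, which would cover a new brain lesion. That is a fair reading, but it belongs to a discontinuation criterion, it conflicts with Section 11.1, and it covers neither symptomatic deterioration nor growth of a known brain metastasis. The last is foreseeable, because Section 3.29i admits patients with treated, stable brain metastases.

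Third, the upward bias is not established by the text. Censoring at first PD is an assumption, and f is unknown; the exclusion of active CNS metastasis at entry may keep it low. This stands, and it is why the figures above are only illustrative.

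Finally, PFS has no test, target or comparator here. That limits the consequence but does not supply the missing rule.

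**Conclusion.** The gap is real. Section 16.34 does not say how CNS progression without a second evaluation, or symptomatic deterioration, enters PFS, and no confirmatory scan is scheduled for either group. As written, these patients may not become PFS events, or may be dated late. Sections 11.1, 11.45, 13.2, 13.3 and 16.34 do not agree on what progression is.

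If such patients were censored at first PD and PFS were exponential, median PFS would be overstated by 11%, 25% or 43% for f of 10%, 20% or 30%. The direction follows from that handling; the size cannot be fixed from the documents.

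The effect is confined to a secondary, descriptive endpoint. The response-rate endpoint, N = 33 and the stated power do not change. The point should be settled before analysis; it does not threaten the trial's main conclusion.

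**What to change.** Put the analysis rule in Section 16.34 only. For the PFS analysis, count as an event, dated at first documentation, the earliest of:

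- (a) RECIST PD that is later confirmed;
- (b) first PD in the CNS;
- (c) first RECIST PD in a patient with no later evaluation.

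State whether symptomatic deterioration under Section 11.45 is an event, and report median PFS both with and without it, since its criteria are partly subjective. State the censoring rule for everyone else.

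Reconcile the wording of Sections 11.1, 11.45, 13.2, 13.3 and 16.34 so that each makes clear whether it governs treatment or the PFS analysis. Do not change the substance of the definition in Section 11.1 to achieve this: the same term feeds the clinical benefit rate (Section 16.33) and the continuation text in Section 13. The treatment-continuation rules and the clinical benefit rate definition stay as they are.

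The cost is wording. First CNS PD and symptomatic deterioration are already reported, so no new data are needed. The downside is that median PFS becomes somewhat shorter, and some unconfirmed PD counted under (c) may be pseudoprogression.

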# Exception: Patients who develop PD in the CNS should discontinue study treatment.

- Request by patient to discontinue study treatment
- Unacceptable toxicity
- Intercurrent illness that would, in the judgment of the investigator, affect assessments of clinical status to a significant degree or require discontinuation of drug
- Administration of radiotherapy, non-protocol chemotherapy, immunotherapy, biological agents, or an experimental drug during the trial
- Development of new primary cancer
- Ineligibility

Patients who discontinue treatment due to progression or development of a second primary, desire for non-protocol treatment, intolerability, patient request, physician decision, or inter-current illness preventing further administration of protocol treatment will proceed to event monitoring phase of the trial where patient and disease status until death or a maximum of 5 years post-registration

# 13.4 Ineligible

A patient is deemed *ineligible* if after registration, it is determined that at the time of registration, the patient did not satisfy each and every eligibility criteria for study entry.

- If the patient received any protocol treatment, all data (except biospecimens) up until the point of confirmation of ineligibility must be submitted. Event monitoring will be required per Section 18.0 of the protocol.
- If the patient never received any protocol treatment, on-study material (except biospecimens) and the End of Active Treatment/Cancel Notification Form must be submitted. No further No further data submission is necessary.

# 13.5 Withdrawn

A patient who withdraws consent before any study treatment is given. On-study material (except biospecimens) and the End of Active Treatment/Cancel Notification Form must be submitted. No further data submission is necessary.

# 13.6 Subsequent Treatment

Subsequent treatment is at the discretion of the attending physician.

# 13.7 Major violation

A patient is deemed a *major violation*, if protocol requirements regarding treatment in cycle 1 of the initial therapy are severely violated that evaluability for primary end point is questionable. All data up until the point of confirmation of a major violation must be submitted. The patient will go directly to the event-monitoring phase of the study. The patient may continue treatment off-protocol at the discretion of the physician as long as there are no safety concerns, and the patient was properly registered. Event monitoring will be required per Section 4.0 of the protocol.

# 13.8 Cancel

A patient is deemed a *cancel* if he/she is removed from the study for any reason before any study treatment is given. On-study material and the End of Active Treatment/Cancel Notification Form must be submitted. No further data submission is necessary.

#### 14.0 Body Fluid Biospecimens

# 14.1 Summary Table of Research Blood/Blood Products to Be Collected for This Protocol

Collect and process all blood/blood products according to instructions and table below. For immunological monitoring both Panel 1 and Panel 2 will be collected.

Correlative Study (Section for more information)	Mandatory or Optional	Blood or Body Fluid being Collected	Component being harvested	Type of Collection Tube (color of tube top)	Volume to collect per tube (# of tubes to be collected)	designated		site? (Yes	
Immune	Mandatory	Whole Blood	Plasma, leukocytes	Heparin (green)	10 mL (7)	х		No	Room temperature
Monitoring				EDTA (purple)	6 mL (1) 4 mL (1)				
Immune Monitoring	Mandatory	Whole Blood	Plasma, leukocytes	EDTA (purple)	6 mL (1)		X 	No	Room temperature

14.11 Collection During Treatment

1. Research blood should be collected per Section 4.0.

2. All specimens should be sent to [name] laboratory c/o [name](pager [name]), [name]

3. Specimens may be collected at any laboratory. If not collected at Mayo Clinic, specimens should be shipped overnight at room temperature to [name] laboratory c/o [name](pager [name]), [name], Mayo Clinic, [name]

# 14.2 Background/Methodology

# 14.21 T cell functional assays

If available, we will keep samples of mDC from each patient and use these cells to stimulate peripheral blood collected as per the test schedule and assay for anti-tumor response via proliferation, ELIspot, or intracellular cytokine expression. We will also stimulate T cells with a cocktail of multiple peptides from common melanoma antigens.

# 14.22 Immune phenotyping

We will immune phenotype blood and tumor for immune cells including but not limited to Tregs, central memory and effector memory T cells, quantitative T, B, and NK cell panel, dendritic cells and immune suppressor cells (CD14+DRneg) and other immune modulating cells per our prior experience. PD-1, PD-L1 and PD- L2 expression on leukocyte subset will be analyzed.

#### 14.23 Tetramer assays

We will compare pre- and post-treatment frequencies of melanoma-specific CD8 T cells via tetramer staining in HLA-A2-positive patients. PBMCs will be labeled with HLA-A2 tetramers complexed with melanoma-associated antigen peptides (MART-127-35, GP100209-217, survivin-- ELTLGEFLKL, and tyrosinase368-376), and control peptides. PBMCs will be counterstained with anti-CD8 (BD Biosciences, San Jose, CA). The stained samples will be analyzed by flow cytometry (FACScan and CellQuest software, Becton-Dickinson).

# 14.24 Plasma cytokine assay

We will profile the plasma cytokine changes as a result of vaccine administration using commercially available cytokine multiplex assays. We will also assess plasma levels of soluble PD-L1 via ELISA.

# 15.0 Drug Information

# 15.1 Pembrolizumab (MK-3475, Keytruda®) (commercial supply)

15.11 Background

Highly selective anti-PD-1 humanized monoclonal antibody which inhibits programmed cell death-1 (PD-1) activity by binding to the PD-1 receptor on T-cells to block PD-1 ligands (PD-L1 and PD-L2) from binding. Blocking the PD-1 pathway inhibits the negative immune regulation caused by PD-1 receptor signaling. Anti-PD-1 antibodies reverse T-cell suppression and induce antitumor responses.

15.12 Formulation

Commercially available for injection 25mg/ml (4ml) [contains polysorbate 80] in a one-vial formulation

15.13 Preparation and storage

Appropriate dose required volume should be added to an IV bag of either 0.9% sodium chloride or dextrose 5% in water, and the final concentration should be between 1 mg/ml to 10 mg/ml. Mix diluted solution by gentle inversion. Discard any unused portion left in the vial. Store bag at room temperature for no more than 6 hours (includes duration of infusion) and refrigerate [2°C to 8°C or 36°F to 46°F] for no more than 24 hours. Allow solution to come to room temperature prior to administration.

15.14 Administration:

Infuse over 30 minutes through a 0.2 to 5 micron sterile, nonpyrogenic, lowprotein binding inline or add-on filter. Do not infuse other medications through the same infusion line. Compatible in either 0.9% sodium chloride or dextrose 5% in water.

15.15 Pharmacokinetic information:

**Note:** Clearance is ~20% lower at steady state than with the first dose. With weight-based dosing (2 mg/kg), pembrolizumab concentrations in pediatric patients are comparable to those of adults (at the same dose). Distribution:  $V_{dss}$ : 6.1 L

Excretion – mean estimated  $t_{1/2}$  values from the 28-day single dose profiles ranged from 14.1 to 21.6 days. Clearance is nonlinear and saturable.

15.16 Potential Drug Interactions

There are no known significant drug interactions.

15.17 Known potential toxicities:

Consult the package inset for the most current and complete information.

Common known potential toxicities, >10%: Cardiovascular: Facial edema Central nervous system: Fatigue Dermatologic: Pruritus, skin rash Endocrine & metabolic: Hyperglycemia, hyponatremia, hypoalbuminemia, hypertriglyceridemia, hypocalcemia, decreased sodium bicarbonate Gastrointestinal: Nausea, decreased appetite, constipation, diarrhea, vomiting, abdominal pain Hematologic & oncologic: Anemia, lymphocytopenia Hepatic: Increased serum AST, increased serum ALT, increased serum alkaline phosphatase Neuromuscular & skeletal: Arthralgia Respiratory: Cough, dyspnea Miscellaneous: Fever

#### Less common known potential toxicities, 1% - 10%:

Central nervous system: Confusion, peripheral neuropathy Endocrine & metabolic: Hypothyroidism, hyperthyroidism Gastrointestinal: Colitis Immunologic: Antibody development Neuromuscular and skeletal: Weakness, arthritis Respiratory: Pneumonitis, pleural effusion, pneumonia, respiratory failure

**Rare known potential toxicities, <1%** (Limited to important or life-threatening):

Adrenocortical insufficiency (immune-mediated), Bullous pemphigoid (immunemediated), chronic inflammatory demyelinating polyradiculoneuropathy, diabetic ketoacidosis, exfoliative dermatitis (immune-mediated), Guillain-Barre syndrome (immune-mediated), hemolytic anemia (immune-mediated), hepatitis (including autoimmune hepatitis), hypophysitis, infusion-related reaction, interstitial nephritis (with renal failure), myasthenia gravis (immune-mediated), myositis (immune-mediated), nephritis (autoimmune), pancreatitis (immune-mediated), partial epilepsy (immune-mediated; in a patient with inflammatory foci in brain parenchyma), thyroiditis, type I diabetes mellitus, uveitis (immune-mediated), vasculitis (immune-mediated)

15.18 Drug procurement:

Commercial supplies. Pharmacist or clinics shall obtain supplies from normal commercial supply or wholesaler.

- 15.19 Nursing guidelines
  - 15.191 Pembrolizumab side effects vary greatly from those of traditional chemotherapy and can vary in severity from mild to life threatening. Instruct patients to report any side effects to the study team immediately. Side effects may be immediate or delayed up to months after discontinuation of therapy. Most side effects are reversible with prompt intervention of corticosteroids.
  - 15.192 Diarrhea can be seen however is less common than that seen with anti-CTLA-4 agents. However it can be severe, leading to colonic perforation. Instruct patients to report ANY increase in the number of stools and/or change in baseline, blood in the stool, abdominal pain to the study team immediately.
  - 15.193 Rash/pruirits/dermatitis is seen. Patients should report any rash to the study team. Treat per section 9.0 and monitor for effectiveness.
  - 15.194 Monitor LFTs closely as elevations in these levels could indicate early onset autoimmune hepatitis. Patients should also be instructed to report any jaundice, or right upper quadrant pain to the study team immediately.

- 15.195 Pneumonitis can be seen and may be mild (only seen on imaging) to severe. Patients should be instructed to report any SOB, dyspnea, cough, chest pain, etc. to the study team immediately. Patients reporting these symptoms should have a pulse ox checked and consider immediate imaging per the treating MD.
- 15.196 Endocrinopathies (including hypopituitarism, hypothyroidism, hypophysitis, and adrenal insufficiency) are seen with this agent. Patients may present only with the vague sense of fatigue and "not feeling well." Additional symptoms may be that of nausea, sweating and decreased activity tolerance. Instruct patients to report these signs or symptoms immediately and obtain appropriate labs as ordered by MD.
- 15.197 Patients who are started on steroid therapy for any side effects of pembrolizumab toxicity should be instructed to take the steroids as ordered, and not to discontinue abruptly as symptoms may return and be severe. Patients may be on steroid therapy for weeks. Instruct patients to report any increase or change in side effects with any dosage decrease as patients may need a slowertaper.
- 15.198 Fatigue is common and may or may not be associated with immune related side effects. Assess patient's fatigue level prior to each cycle of therapy and report any changes to the study team.
- 15.199a Patients should avoid receiving live vaccines within 30 days of study drug administration or per other study guidelines.
- 15.199b Patients who have undergone an allogeneic bone marrow transplant have an increased risk of severe complications including early GVHD and venoocclusive disease, if they have previously been treated with pembrolizumab.
- 15.199c Myocarditis has been reported and associated with pembrolizumab. Instruct patients to report chest pain, SOB, or dyspnea to study team immediately and/or seek emergency medical attention.
- 15.199d Autoimmune hematologic disorders including ITP and hemolytic anemia have been reported. Monitor blood counts closely and report any abnormalities to the study team.
- 15.199e Rare neurologic disorders including Guillain-Barre syndrome and myasthenia gravis have been reported. Instruct patients to report any neurologic symptoms including weakness, parasthesias or numbness, tingling to the study team immedicately.

Protocol version: 03Jul2019

